## ***Biochemical Test:***

### 1. 12 Panel Urine Drug Test Cup (Prime Screen™ or a compatible alternative)

## ***Neurophysiologic measurements:***

[figure not shown]
1. EEG/ERP will be performed using a commercial active 32-electrode system (Biosemi). Before every session a participant will be fitted with a comfortable cap matching their head size. Conductance will be enhanced through the use of the standard EEG gel, which will be injected into the electrodes using plastic syringes with plastic tips. The experimental system will be powered by a low-voltage battery to avoid electrocution.
2. GSR will be measured using a common commercial system ((Biosemi) using two electrodes and applying low voltage between them. The electrodes will be attached to the palm of the dominant hand. The device will be powered by a low-voltage battery.

3. ECG will be measured by a common commercial system (Biosemi) consisting of one active electrode attached to the dominant hand. EMG will be measured by a common commercial system (Biosemi) consisting of two active pair of electrodes attached to participants face above right brow to measure corrugator activity and on the right cheek to measure zygomatic activity. Alternatively the electrodes may be placed on the participant's dominant hand to measure arm muscles' activity.

***Self-reports:***

1. Self-assessment manikin (SAM):

Using a computerized questionnaire, participants will rate their subjective physiological arousal level by selecting one of the 5 figures representing decreasing levels of arousal (Bynion & Feldner, 2017; Handayani et al., 2015).

2. Visual analogue scale (VAS)\*:

Participants will rate their experienced pain level on a standard computerized scale by choosing a point on a line (Ergin et al., 2015; Jamison et al., 2002).

[figure not shown]
3. The Perceived Stress Scale (Cohen, 1988):

A 14-item scale to measure general mental wellbeing (see attached).

4. Demographic/situational questionnaire to access basic demographic information and compliance with the experimental requirements.

***Dynamic visual stimulation:***

DVN will consist of 15-second-long non-figurative dynamic visual patterns (see screenshot examples bellow):

Screenshots from a visual stimulation clip.

## **DATA AND SPECIMEN BANKING**

The personnel responsible for collecting and storing data will be specified in the site-specific protocols. The PI is responsible for all information collected on subjects enrolled in this study. All data collected during this study must be reviewed and verified for completeness and accuracy by the PI. PI will prepare and maintain adequate and accurate source documents designed to record all observations and other pertinent data for each subject participating in the study. In general data obtained from the participants will be recorded and stored in a HIPAA-compliant manner by a designated staff member. Subjects will not be identified by name in the study database or on any study documents to be collected by the Sponsor (or designee), but will be identified by a site number, subject number and initials. All questionnaire results will be coded as to the identity of the study participants in a HIPAA-compliant manner and therefore the study participants will not be identified with the recorded data. No such identifying information will be shared with anyone outside of the study sites. Obtained de-identified data will be used in secondary analyses. The consent form will include a request for secondary data utilization without an expiration date. All team members will be trained and certified in the HIPAA requirements for research involving human subjects.

## **DATA MANAGEMENT**

Data obtained from the participants will be recorded and stored in a HIPAA-compliant manner. Specifically, the data will be de-identified and ID numbers assigned by the responsible investigator at the site will be used.

Dandelion Science Corp intends to share the analysis results with the NIH and appropriate organization/entities that have oversight (e.g., IRB, safety officer). Any data that falls under the

Dandelion Science Corp intellectual property will not be shared. Prior to any type of sharing, Dandelion Science Corp will de-identify and strip data of any information that can link the data with a particular participant. All the data will be stored and transferred in a HIPAA-compliant manner. The de-identified data may be shared in a HIPAA-compliant fashion with consultants and contractors who have a signed confidentiality agreement with Dandelion Science Corp.

#### ***EEG data preprocessing:***

Cleaning EEG data involves removing artifacts from the EEG signal. Although the EEG system is designed to record neural activity, it also records electrical activity arising from physiological entities such as eye blinking or jaw clenching. The EEG will be digitized continuously at a 512 Hz sampling rate. Data will be downsampled to 256 Hz and bandpass filtered using a 0.1 Hz high-pass cut-off (12db/octave) to reduce low-frequency noise such as drifting, and a 30 Hz low-pass cut-off (24db/octave) to reduce high-frequency noise such as muscle tension. Following this step, data will then be re-referenced to the average of all channels. Then a time-frequency analysis will be performed to extract temporal dynamics of the major EEG wave bands (alpha, beta, theta and gamma). Signal processing will be performed using the MNE toolbox (Gramfort et al., 2013) and performed in Python. In addition, the painful stimulation-onset ERPs will be computed and the areas of N2 and P2 components will be used for the analysis.

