## OBJECTIVES

The objective of the current research is to develop a visual stimulation platform capable of modulating nociception and alleviating perceived pain intensity. Dandelion Science (the Sponsor) hypothesizes that controlling the level of arousal through DVN can reduce nociceptive effects caused by experimentally produced painful stimuli in healthy participants.

[figure not shown]
- Aim 1: Find dynamic visual stimuli capable of reliably modulating physiologic arousal.

- Aim 2: Validate EEG, GSR, ECG, and EMG, biomarkers of pain.

- Aim 3: Demonstrate that optimized DVN can modulate nociception and mitigate or modify pain perception in healthy participants\*.

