## ***Data Analysis***

### *Optimization method*

In the optimization procedure, Dandelion Science defines the visual stimulation (VS) parameters and, while they are presented, monitor the response to them. Once the response is registered, we select the next set of parameters that is expected to achieve one or more of the following goals:

- identify and explore in detail VS parameters that affect a specific biomarker (i.e. that cause a significant shift in the biomarker in comparison with its baseline value);
- find the specific values for VS parameters that drive a combination of biomarkers to a predefined state (“target state”);
- improve our general predictive model of the relationship between VS parameters and bioresponse.

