#### ***Optimization training and testing\*:***

During the optimization procedure, we will use alpha and beta EEG bands, number of peaks in GSR, heart-rate variability and facial EMG spectrum, among other features, to guide the arousal and pain-control optimization procedure. The success of the optimized stimuli in reducing pain

perception will be evaluated using VAS. Prior data indicate that the minimal clinically relevant change in pain self-report should be 20%. In our study this effect will correspond to roughly an 8 mm change on the 100mm VAS. If the true difference in the mean response of matched pairs is 8 mm, we will need a sample of 30 participants to be able to reject the null hypothesis that the response difference is zero with a probability (power) of 0.8. The Type 1 error probability of this test is 0.05.

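### The EEG plan low-pass filters at 30 Hz and then extracts gamma from the same data without giving band limits; if gamma starts near 30 Hz, most of it is filtered out first

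*Combined protocol and SAP*

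**What the plan says.** The section on EEG data preprocessing sets out a single chain. The signal is digitized at 512 Hz, downsampled to 256 Hz, and band-pass filtered with a 0.1 Hz high-pass and "a 30 Hz low-pass cut-off (24db/octave) to reduce high-frequency noise such as muscle tension". The next sentence begins "Following this step, data will then be re-referenced to the average of all channels". A time-frequency analysis comes after that, to "extract temporal dynamics of the major EEG wave bands (alpha, beta, theta and gamma"). The N2 and P2 areas are obtained in addition.

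No section describes a second EEG stream with a wider pass-band, and none gives frequency limits for any band.

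Three other places bear on how gamma might be used:
- Aim 2 in the Objectives is to "Validate EEG, GSR, ECG, and EMG, biomarkers of pain".
- Optimization training and testing says "we will use alpha and beta EEG bands, number of peaks in GSR, heart-rate variability and facial EMG spectrum, among other features". Alpha and beta are the only EEG bands named there, and success on pain is judged by VAS.
- The Experiment 1 optimization method looks for stimulation parameters "that cause a significant shift in the biomarker in comparison with its baseline value". It does not say whether the comparison with baseline is made at each frequency.

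**The concern.** Gamma is commonly taken to begin at about 30 Hz. On that reading, the plan first suppresses the range above 30 Hz as noise and then measures the same range as a brain signal. An analyst who follows the text exactly will still get a number labelled gamma, because a 24 dB/octave slope leaves a residue just above the cut-off. The risk is therefore mislabelling rather than a missing value. A null gamma result could reflect the filter, and a positive one could reflect activity close to the edge of beta. This matters for Aim 2, where EEG features are candidates for validation as pain biomarkers, and for the optimizer only if gamma enters through the open-ended part of its feature list.

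**Working it through.** The plan states no figure for retained power, so there is nothing to reproduce. The check is what a filter with the stated cut-off and slope does.

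**From the plan:** cut-off 30 Hz; slope 24 dB/octave; sampling rate after downsampling 256 Hz, so the Nyquist limit is 256/2 = 128 Hz.

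**Assumed:** Butterworth design (no other family was tried); gamma as 30-45 Hz or 30-80 Hz; input power spectrum S(f) flat, 1/f or 1/f².

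**Step 1, power gain G(f).** Two designs give 24 dB/octave in total:
- Order 4, single pass (analogue form): G = 1/(1 + (f/30)^8). At 40 Hz, (40/30)^8 = 9.99, so G = 1/10.99 = 0.091. The digital form at 256 Hz gives 0.069.
- Order 2, forward and backward (analogue form): G = [1/(1 + (f/30)^4)]². At 40 Hz, (40/30)^4 = 3.16, so G = (1/4.16)² = 0.058. The digital form gives 0.046.

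Across these forms the power left is 25-50% at 30 Hz, 11-23% at 35 Hz, 5-9% at 40 Hz, 0.7-1.7% at 50 Hz and 0.1-0.4% at 60 Hz.

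**Step 2, raw power summed over the band.** Fraction kept = ∫S·G / ∫S over the band. The 30-40 Hz share is ∫S·G over 30-40 Hz divided by ∫S·G over the band. If 50-80 Hz power doubles, band power rises by ∫S·G over 50-80 Hz divided by ∫S·G over the band. For a flat unfiltered spectrum on 30-80 Hz these are 10/50 = 20% and 30/50 = 60%. Ranges below cover the three spectra and, where filtered, the digital and analogue forms.

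| Quantity | Unfiltered | Order 4, single pass | Order 2, forward-backward |
|---|---|---|---|
| 30-45 Hz power kept | 100% | 17-22% | 9-12% |
| 30-80 Hz power kept | 100% | 5-12% | 3-7% |
| 30-40 Hz share of 30-80 Hz | 20-40% | 82-93% | 77-90% |
| Rise in 30-80 Hz if 50-80 Hz doubles | 36-60% | 0.6-3.8% | 1.0-5.7% |
| Rise in 30-45 Hz if 40-45 Hz doubles | 25-33% | 5-11% | 7-13% |

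**Step 3, sensitivity to the lower limit** (order 4, single pass). With an upper limit of 80 Hz, power kept is 11-25% from 25 Hz, 2-5% from 35 Hz and about 1-2% from 40 Hz. Most of the band is lost wherever gamma is started between 25 and 40 Hz.

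**Step 4, where the effect is smaller.**
- Change across the whole band, raw power: G is fixed, so doubling every frequency doubles the filtered sum too (ignoring noise added later). The relative change survives.
- Power normalised at each frequency (Morlet wavelets, digital order 4, single pass), all of 30-45 Hz doubled: the feature rises 75-78% against 78% unfiltered at 7 cycles, about 85% against 84% at 10 cycles, and 56-65% against 68-70% at 5 cycles.
- Same normalisation, 30-80 Hz band, only 50-80 Hz doubled: 40-44% against 52-53% at 7 cycles, 52-53% against 54-55% at 10 cycles, but 15-23% against 47-50% at 5 cycles. Short wavelets let power from below 40 Hz leak into the higher frequencies, so normalisation does not fully cancel the filter.

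**The case against.** The best counter-argument is that nothing planned depends on gamma. The word appears once, in a list of bands. The optimizer names alpha and beta, the ERP analysis uses N2 and P2, and pain success is judged by VAS. Aim 2 says EEG, which those other features could satisfy without gamma. This stands, and it is why the point is minor.

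A second argument is that the text alone shows no flat contradiction, since no band limits are given and the slope is gradual. This also stands: the point needs the assumption that gamma starts near 30 Hz. But the missing limits are themselves a gap, and most of the band is lost for any start between 25 and 40 Hz.

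A third argument is that normalising to baseline at each frequency cancels a fixed filter gain. That is largely right with wavelets of 7 or more cycles and only partly right with 5. The plan specifies neither the normalisation nor the wavelet width, so it cannot rely on this.

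A reader might go further and infer that gamma is wiped out altogether. Under per-frequency normalisation, a near-total loss (a 0.5-1.2% response to a doubling at 50-80 Hz with 5 cycles) appears only when an order-4 filter is run forward and backward. That is 48 dB/octave in total, whereas the plan says 24. It would apply only if the stated slope described each pass separately, which the text does not say.

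**Conclusion.** The point holds in a limited form. As written, the plan takes gamma from data already low-passed at 30 Hz and gives no band limits. If gamma starts near 30 Hz and the filter is a Butterworth of 24 dB/octave in total, roughly 80-90% of 30-45 Hz power and 88-97% of 30-80 Hz power is removed. A raw-power gamma feature is then mainly a 30-40 Hz measure and barely responds to change above 50 Hz. How far a normalised feature is distorted depends on wavelet width and filter direction, which the plan leaves open.

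The consequence is minor. It touches Aim 2, and the optimizer only if gamma is used there. One might infer that the study's pain result is compromised; the documents do not support that. The VAS evaluation, the N2/P2 areas, the named alpha and beta features and the sample size do not use gamma.

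**What to change.** State the limits of every EEG band in Hz in the preprocessing section, and then do one of two things.

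1. **Delete gamma from the band list** and keep 0.1-30 Hz throughout. This is a one-word edit. The cost is giving up gamma as a candidate biomarker under Aim 2.
2. **Compute gamma from a separate branch.** Keep 0.1-30 Hz for the N2/P2 ERPs, and give the gamma branch a low-pass above the stated upper limit of gamma and below 128 Hz. This is a software change in the existing MNE/Python pipeline and needs no new recording, since the raw signal is digitized at 512 Hz.

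The second option readmits the muscle noise that the 30 Hz cut-off was meant to reduce, and mains noise if the band reaches that frequency. The section lists artifacts "such as eye blinking or jaw clenching" but describes no muscle-specific step beyond the low-pass, so a rule for both noise sources should be fixed before conditions are compared. EMG electrodes "attached to participants face above right brow to measure corrugator activity and on the right cheek to measure zygomatic activity" could serve as a muscle reference, but only in sessions with that placement, because the plan also allows them on the hand. Stating the wavelet or window width, the normalisation and the filter direction would make the feature reproducible, though this goes beyond what is needed to reconcile the cut-off with the band list.

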#### ***GSR data preprocessing:***

First, GSR artifacts will be detected by automatically identifying large, sharp changes in the amplitude, defined as an absolute value change of the derivative larger than 10. These artifacts will be corrected using cubic splines. Then the tonic and phasic components will be separated through FIR filtering. Then through application of a threshold a number of peaks will be calculated.

#### ***ECG data preprocessing:***

The ECG data will be downsampled to 500 Hz. The QRS complex will be identified using Hilbert transform procedure and the R-R intervals will be computed.

#### ***EMG data preprocessing:***

Analog band pass filter (20Hz to 500 Hz) will be applied to the raw signal before it is digitized. Then wavelet transform will be used to perform a time-frequency analysis on EMG data.

#### ***Optimization training and testing\*:***

During the optimization procedure, we will use alpha and beta EEG bands, number of peaks in GSR, heart-rate variability and facial EMG spectrum, among other features, to guide the arousal and pain-control optimization procedure. The success of the optimized stimuli in reducing pain

perception will be evaluated using VAS. Prior data indicate that the minimal clinically relevant change in pain self-report should be 20%. In our study this effect will correspond to roughly an 8 mm change on the 100mm VAS. If the true difference in the mean response of matched pairs is 8 mm, we will need a sample of 30 participants to be able to reject the null hypothesis that the response difference is zero with a probability (power) of 0.8. The Type 1 error probability of this test is 0.05.

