## STUDY-WIDE NUMBER OF PARTICIPANTS

Up to 120 participants

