## STUDY ENDPOINTS\*

Successful control of the arousal reduction of pain perception as measured by VAS and ERP for either thermal (CHEPs) or electric shock pain induction. While there is no single criterion for determining a clinically significant threshold, Dandelion Science has adopted the reported criterion of 20% reduction in pain intensity and expects to achieve a pain perception reduction of 20% on VAS scale for AI-guided visual stimulation as compared with no-visual-stimulation in response to at least one of the nociceptive conditions (CHEPs stimulation).

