### Equipment and instruments

1. Neurophysiologic assessment: EEG, GSR, EMG, ECG
2. Behavioral assessment: self-assessment manikin (SAM)
3. Visual stimulation: DVN presented on a display
4. Infrastructure: 2 laptops / PCs for rendering & processing of the data

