### ***Pilot***

To assess the effectiveness of the optimization process, a baseline response will be collected to serve as a control condition. Prior to the main experiment we will run a pilot experiment on 5 to 10 participants following the same structure as in the main experiment but with the visual stimulation parameters being chosen randomly during each iteration.

In addition, up to 5 participants will take part in pilot experiments with the cold pressor test (Lamotte et al., 2021), a simple and validated test that has been used in clinical and research settings to evaluate non-baroreflex-mediated sympathetic neural control in humans. During the test the subject immerses one hand or foot into ice water for up to 3 min while blood pressure and heart rate are monitored.

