## **Experiment 2. Optimization of visual stimulation for pain perception**

In this experiment we will optimize visual stimulation with the goal of reducing pain perception. To reduce the burden on participants, optimization has been designed as a two-step process, with the first step (implemented in Experiment 1) requiring no pain induction. Our preliminary hypothesis is that arousal-inducing visual stimuli will reduce the perception of acute pain, based on the well-known phenomenon of stress-induced analgesia (Vachon-Presseau et al., 2013; Yilmaz et al., 2010). Thus, once we optimize the stimuli to affect arousal state in Experiment 1, we will test the effectiveness of the optimized visual stimuli (OVS) in reducing pain perception and carry out additional adjustments to further increase their impact.

Location	Dandelions Science Laboratory 
Estimated number of participants	20 participants
Estimated experiment duration	2 hr

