### ***Equipment and instruments***

1. Neurophysiological assessment: EEG, GSR, EMG, ECG
2. Behavioral assessment: VAS

3. Visual stimulation: DVN presented on a display
4. Infrastructure: 2 laptops / PCs for rendering & processing of the data
5. Nociception: Contact Heat Evoked Potentials (CHEPs)

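### The only power calculation calls for 30 participants on the pain VAS, but the experiment that measures it plans 20, which gives about 61–65% power instead of 80%

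*Combined protocol and SAP*

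**What the plan says.** The sample-size statement is in Optimization training and testing, under Data Management. It equates a 20% change in self-reported pain with roughly 8 mm on the 100 mm VAS. It then says that "we will need a sample of 30 participants to be able to reject the null hypothesis", for matched pairs, at 80% power and a type 1 error of 0.05. It gives no SD of the paired differences and does not say whether the test is one- or two-sided.

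The enrolment figures are elsewhere:

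- Experiment 2 (pain): estimated enrolment of "20 participants".
- Experiment 1 (arousal): up to 100.
- Study-wide: "Up to 120 participants".

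The equipment lists show where the VAS is used. Experiment 2 has "Behavioral assessment: VAS" and the contact-heat stimulator. Experiment 1 uses the self-assessment manikin, and the Goals section says it needs no pain induction. Experiment 1 does include a cold pressor pilot ("up to 5 participants will take part in pilot experiments with the cold pressor test"), but the monitoring described there is blood pressure and heart rate, not VAS.

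Under Study Endpoints, the sponsor "expects to achieve a pain perception reduction of 20% on VAS scale" relative to no visual stimulation.

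**The concern.** A VAS test of pain reduction can only be carried out in Experiment 2, so the 30 must refer to that experiment, which plans 20. The 20 does not look like a slip, because 100 + 20 matches the study-wide ceiling of 120.

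This is the only sample-size justification in the plan. It supports the VAS part of the endpoint and Aim 3, which is to demonstrate an effect on pain. If 20 people are enrolled, the study has a higher risk of missing an effect of the size the plan itself calls clinically relevant. A null result would then be read against a power of 80% that the design did not have.

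**Working it through.** **Inputs from the plan.** Difference δ = 8 mm; matched pairs; α = 0.05; power 0.80; required n = 30; planned n = 20.

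**Not in the plan.** SD of paired differences, sidedness, dropout allowance. The figure of 30 therefore cannot be reproduced independently. The check instead asks which SD makes 30 correct, and then what that SD implies for 20. No dropout is applied.

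**Formula.** For a paired t-test, the noncentrality is λ = (δ/SD)·√n on n − 1 degrees of freedom. Power is the probability that a noncentral t variable falls beyond the critical value.

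**Step 1: SD implied by n = 30.**
- Two-sided: 80% power at n = 30 needs δ/SD = 0.529, so SD = 8/0.529 ≈ 15.1 mm.
- One-sided: δ/SD = 0.465, so SD = 8/0.465 ≈ 17.2 mm.
- If 30 was rounded up from just over 29, the SD could be as low as 14.8 mm (two-sided) or 16.9 mm (one-sided).

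**Step 2: power at n = 20 with the same SD.**
- Two-sided: λ falls from 0.529 × √30 = 2.90 to 0.529 × √20 = 2.37, and power falls from 0.80 to 0.613.
- One-sided: λ falls from 0.465 × √30 = 2.55 to 0.465 × √20 = 2.08, and power falls from 0.80 to 0.640.

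| Test | Implied SD (mm) | Power at n = 20 | Difference with 80% power at n = 20 (mm) |
|---|---|---|---|
| Two-sided | 14.8–15.1 | 0.613–0.628 | 9.80–9.98 |
| One-sided | 16.9–17.2 | 0.640–0.654 | 9.75–9.93 |

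The chance of missing a true 8 mm effect is therefore 1 − 0.654 = 0.35 to 1 − 0.613 = 0.39. At n = 25, two-sided power would be 0.72–0.73.

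**Step 3: scale.** If 8 mm is 20%, the implied baseline is 8/0.20 = 40 mm. A detectable difference of about 10 mm is then 10/40 = 25%.

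**Step 4: could 20 be enough?** Keeping 80% power for 8 mm at n = 20 needs an SD of at most 12.1 mm (two-sided) or 13.9 mm (one-sided). With either, 30 would not be needed, so no single SD makes both figures right.

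**Step 5: does the method matter?** With the normal approximation, power = Φ(δ√n/SD − z).
- Two-sided: δ/SD = (1.960 + 0.842)/√30 = 0.511 and SD = 15.6 mm. At n = 20, power = Φ(0.511 × √20 − 1.960) = 0.628, or 0.643 allowing for rounding from 29.
- One-sided: 0.650, or 0.663 allowing for rounding.
- If 30 came from the two-sided normal formula and the 20 participants are then analysed with a t-test, power is 0.58–0.60.

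Across all these combinations the range is about 0.58–0.66.

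**Step 6: enrolment.** 100 + 20 = 120 as planned. Thirty in Experiment 2 would fit under the ceiling only if Experiment 1 enrolled 90 or fewer (90 + 30 = 120). Both sums take the pilots as part of Experiment 1.

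**The case against.** The strongest reply is that nothing is miscalculated. The 20 is labelled an estimate, the other figures are upper limits, and 30 could be accommodated. Without an SD, 30 can be neither confirmed nor refuted, and every power figure for 20 comes from an SD solved from the number in dispute. This is fair as a limit on precision: about 60–65%, conditional on the plan's own calculation, is as much as can be supported. It does not remove the contradiction, which needs no SD. No section commits to 30 or explains the gap.

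A second reply is that this is early, exploratory work, and that Experiment 2's listed goals concern finding stimuli and tracing an optimization curve. That is true of much of it. But the plan also sets a 20% VAS target, aims to demonstrate an effect on pain, and makes a formal power claim for it.

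Three smaller points stand:

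- The null hypothesis of zero difference favours the two-sided reading, so 61–63% is the better paired-t range.
- The Pilot section describes 5 to 10 participants plus up to 5 more, and does not say outright that they count within Experiment 1's 100. If they do not, the enrolment sums change by up to 15.
- Experiment 2's Conditions section lists optimized stimulation only, while the endpoint compares it with no visual stimulation. Correcting the number does not settle where the paired comparator comes from. That is a separate matter.

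**Conclusion.** The concern holds. It is an inconsistency between two stated numbers: the power statement requires 30, and the only experiment it can apply to plans 20. If the plan's calculation is taken as right for a paired t-test, power at the planned size is about 61–65%, not 80%. Other plausible methods widen this to about 58–66%, and none approaches 80%. These sizes rest on an 8 mm true difference, an SD inferred from the plan's 30, and no dropout. The plan makes no dropout allowance although participants may stop at any time, so losses would lower power further. This must be fixed, because it is the only sample-size justification in the plan.

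**What to change.** Restate the power paragraph in Optimization training and testing for the planned sample, with the sponsor's own SD and the sidedness of the test. For example:

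> With 20 participants, an SD of paired differences of [sponsor's value] mm and a [one-/two-]sided type 1 error of 0.05, the power for an 8 mm difference is [x], and 80% power is reached for a difference of [y] mm.

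With the two-sided SD implied by the current text (about 15.1 mm), x is about 0.61 and y about 10 mm. These values only illustrate the scale, since that SD is derived from the disputed 30. The change is wording only; its cost is a less favourable stated power and the need to supply an SD.

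If the sponsor instead wants 80% power for 8 mm on the current calculation, the Experiment 2 figure would have to become 30. Lowering Experiment 1 to at most 90 would keep the ceiling of 120, provided the pilots count within Experiment 1. In that case 10 more people would undergo pain induction, although the plan gives reduced participant burden as the reason for the two-stage design, and Experiment 1 would lose 10 places. That choice is the sponsor's. Either way, the power paragraph, both experiments' enrolment figures and the study-wide number should agree.
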